## Protocol Version and Amendment Tracking

Version	Date	Brief Summary of Changes
1.0	21/DEC/2023	Original Protocol
1.1	18/MAR/2024	Updated administration timeline for the NIH Toolbox Social Relationship scales (i.e., removed Week 2 assessment point), added in details for an optional post trial user experience interview, and added clarifying language around safety monitoring procedures.

## Protocol Synopsis

Protocol Number:	W-DISC-002
Full Title:	An Exploratory Open-Label Potency and Precision Investigation of a Relational Agent Intervention
Abbreviated Title:	PAPI: Potency and Precision Investigation
Sponsor:	Woebot Health
Study Type:	Product learning
Number of Participants:	200
Number of Sites:	1
Study Objective:	The overarching goal of this study is to establish initial proof of mechanism for precision interventions in an adult population.
Primary Aim and Endpoint:	Aim: Describe therapeutic alliance with Woebot at week 1 and week 4 of the intervention.  Endpoints: 

Working Alliance Inventory (WAI) total score at week 1 and WAI total score at week 4.

Secondary Aims and Endpoints:	N/A
	[REDACTED]

	
	
Study Design:	Single arm pilot study
Study Duration:	4 week intervention period
Target Population:	Adults between the ages of 18 and 75 years experiencing at least mild depression or anxiety symptoms.
Key Inclusion Criteria:	

1. Adults 18 - 75

2. Has regular access to a smartphone (Android or iOS smartphone with a recent supported operating system) with reliable WiFi access or sufficient data to engage with assigned study arm for the duration of the study

3. Available and committed to engage with the program and complete assessments for study duration

4. Able to read and write in English

5. U.S. resident

6. PHQ-8 > 4 and/or GAD-7 > 4, assessed at Screening/Baseline

Key Exclusion Criteria:	

1. Current suicidal ideation with a plan and/or intent or a suicide attempt within the past 12 months

2. Previous Woebot use

3. Involuntary inpatient psychiatric hospitalization any time within the past 30 days

4. Lifetime diagnosis of bipolar disorder

5. Lifetime diagnosis of a psychotic disorder

Study Condition:	DISC-MA

Test Device:	DISC-MA
Control Device:	N/A
Statistical Methods:	
Descriptive statistics will be reported for study measures. Summary reports will be presented for all time periods independently. [REDACTED]
 
[REDACTED]
 
[REDACTED]
 
[REDACTED]
 
Bivariate analyses will use chi-squared tests, Fisher exact test, t-tests, one-way ANOVA, Person's correlation, and Spearman's correlation, where applicable. No hypothesis testing will be completed, and only effect sizes and 95% confidence intervals will be provided where applicable. For departures from normality, the appropriate non-parametric method will be applied.

Protocol Version and Date:	1.1 (18 /MAR /2024 )
Keywords:	digital mental health intervention, chatbot, conversational agent, relational agent, natural language processing, artificial intelligence

**Table 1. Schedule of Events**

Visit Weeks/Days	Screening Period	Intervention Period		
	Screening / Baseline Day -14 to Day 1	Week 1 Day 7 (+6)	Week 2 Day 14 (+6)	Week 4 Day 28 (+6)
Informed Consent (asynchronous e-Consent via Citrus)	X			
Participant Identity Verification a	X			
Eligibility Confirmation (inc/exc) b	X			
Demographics b	X			
Medical History   Prior & Concomitant Medications/Therapy b	X			
Medical History   Psychiatric History b	X			
The Accountable Health Communities Health-Related Social Needs Screening Tool b	X			
███████████	█	█	█	█
███████████	█	█	█	█
███████████	█	█	█	█
███████████	█		█	█
██████	█	█	█	█
██████	█	█	█	█
██████	█	█	█	█
App Download / Registration c	X			
Working Alliance Inventory (WAI-SR) b		X		X
Safety Survey b			X	X
Assessment of AE/SAEs				X
Enactment c				X
App Engagement Metrics c				X
Termination of App Access c				X
Estimated Time to Complete	45 minutes	15 minutes	30 minutes	30 minutes

## 1. Introduction

### 1.1 Background

[figure not shown]
Precision medicine is defined by the Food and Drug Administration as “...to target the right treatments to the right patients at the right time”. In the context of mental health, the goal of a precision medicine approach is to use the various tools and data to develop more effective and safe treatments. Digital mental health interventions are uniquely positioned to create and deliver precision interventions that follow this FDA definition by being able to deliver in a standardized way fit for purpose interventions that target mechanisms for specific users at specific moments of the user journey.

### 1.2 Study Rationale

The overarching goal of this study is to inform the development of precision interventions within the Woebot for Mood and Anxiety investigational product. This study will provide initial learning on the current implementation of precision interventions and generate data and hypotheses to inform the exploration of future interventions by identifying mechanisms and moments in the user journey to target.

### 1.3 Investigational Device

DISC-MA is a discovery version (3.2) of the investigational product Woebot for Mood and Anxiety and is a non-prescription digital software device, accessible via iOS and Android smartphone operating systems.

[figure not shown]

## 2. Objectives

### 2.1 Primary Aim

- Describe therapeutic alliance with Woebot at week 1 and week 4 of the intervention.
- *Primary Endpoints:*
  - *Working Alliance Inventory (WAI) total score at week 1 and WAI total score at week 4.*

### 3. Study Design

[figure not shown]
#### 3.1 Description of Trial Design

This study is a single arm pilot trial aimed at exploring and informing precision interventions within the Woebot for Mood and Anxiety investigational device. Study participation is up to 7 weeks in total, including a 2 week screening/baseline phase, followed by a 4 week active intervention phase, and 1 week to complete the final study survey.

Participants will be recruited and enrolled into the study by Lindus Health. All remaining data collection and study monitoring will be managed through the Citrus decentralized trial platform managed by Lindus Health and by designated Woebot Health study personnel.

Self-report survey assessments will be administered to all participants at Screening/Baseline, Week 1, Week 2, and Week 4. Members of the study team may contact participants through the Citrus platform via phone/sms and/or email to remind participants to complete study activities.

**Figure 2: Participant Journey Flowchart**

### 3.2 Rationale for Trial Design

This trial design will allow for characterization of participants at baseline in order to better understand and generate hypotheses about how these characteristics interact with patterns of engagement within the Woebot for Mood and Anxiety investigational product.

## 4. Trial Intervention

### 4.1 Study Condition

All participants will have access to the same trial intervention, DISC-MA, for 4 weeks. The trial intervention will be accessed through a mobile app and will be made available exclusively for study participants through unique access codes.

#### 4.3 Trial Intervention Compliance

Participants will be removed from the study and considered a “screen failure” for failing to register for the app by Day 3. Trial intervention compliance will not be monitored during the live trial and participants will not be withdrawn for not regularly engaging with their assigned treatment. Instead, intervention compliance will be assessed post study during analysis. Compliance may be defined as opening the app at least once per week for a minimum of 50% of weeks (2 of 4) during the intervention period.

#### 5. Study Population

Participants will be recruited through the Lindus Health CitrusRecruit network which utilizes a combination of participant sources including but not limited to existing patient databases, primary care networks, and targeted social media campaigns. Those interested in participating will be invited to complete a survey to confirm they meet the pre-screening criteria and be presented with the opportunity to independently review and electronically sign the study consent form. Upon signing the consent form, participants will be asked to schedule a video call during which a designated member of the Lindus Health trial team will verify the participants identity. After successful completion of the verification call, participants will be provided with a secure link to complete the screening/baseline survey. In order to further assess eligibility, participants will be asked questions about their medical history including self-report of (1) any involuntary inpatient psychiatric hospitalizations within the past 30 days, (2) a lifetime diagnosis of bipolar disorder, (3) a life time diagnosis of a psychotic disorder, and

(4) current suicidal ideation with plan and/or intent or an attempt in the past 12 months. People who do not meet study criteria based on these additional exclusionary criteria will be notified that they may benefit from a level of care beyond the scope of the study and that if they feel they are in need of immediate medical care they should contact 911 or go to their nearest emergency room and reach out to someone they trust and that can help them stay safe. Additional resources will also be provided electronically. If a participant endorses presence of **current** suicidal plan and/or intent, the study PI will attempt to follow-up with the participant (up to three times). See Section 8.5.1 of this protocol for more details.

## 5.1 Selection of Study Population

The study aims to enroll approximately 200 adults between the ages of 18 and 75 years experiencing at least mild depression or anxiety symptoms into the study. An enrolled participant is defined as a participant that meets all eligibility criteria as described below and registers in the app by Day 3 of the study.

### 5.1.1 Inclusion Criteria

In order to be eligible to participate in this study, an individual must meet all of the following criteria:

1. Adults between the ages of 18 and 75 years
2. Own or have regular access to a smartphone with a recent operating system installed (Android: OS 8.0 or higher, Apple: iOS 13.0 or higher) with reliable Wi-Fi access or sufficient data plan to engage with assigned treatment condition for the duration of the study
3. Available and committed to engage with the program and complete assessments for a 4-week duration
4. Able to read and write in English
5. U.S. resident
6. PHQ-8 > 4 and/or GAD-7 > 4, assessed at screening/baseline

### 5.1.2 Exclusion Criteria

An individual who meets any of the following criteria will be excluded from participation in this study:

1. Current suicidal ideation with a plan and/or intent or a suicide attempt within the past 12 months
2. Previous Woebot use
3. Involuntary inpatient psychiatric hospitalization any time within the past 30 days
4. Lifetime diagnosis of bipolar disorder
5. Lifetime diagnosis of a psychotic disorder

## 5.2 Screen Failures

Participants who sign study consent and (1) do not meet inclusion/exclusion criteria or (2) fail to register in the app by Day 3, will be considered a Screen Failure. Participants will be notified that they did not meet eligibility criteria and provided with a set of resources. Re-screens will not be permitted in this study. De-identified participant ID numbers assigned to participants who screen fail will not be reused.

### **5.3 Withdrawal of Participants from the Study**

If a participant decides to withdraw consent from the study, they will be removed from future study activities and any data collected before withdrawal may be retained and used in study analyses. In addition, a participant may be withdrawn by the investigator if the participant violates the study plan, or for administrative and/or other safety reasons.

Discontinuation of study treatment for a participant occurs when study treatment is stopped earlier than the protocol planned duration and can be initiated by either the participant or the investigator. The investigator must discontinue study treatment for a given participant if he/she believes that continuation would negatively impact the participant's well-being. Involvement in the study is strictly voluntary. Participants have the right to withdraw from the study at any time for any reason, without any reprisal.

Participants should be discontinued from the study if any of the following occur:

1. It is discovered that the participant shared app images/screenshots publicly
2. The participant withdraws consent to participate in the study
3. The participant develops an illness that would interfere with their continued participation in the study
4. The participant has an SAE rated as Grade 3 (severe) or higher (see Section 8.3.2)
5. The participant is noncompliant with treatment schedule, study procedures, in the opinion of the investigator and per the protocol, where applicable
6. The PI, Sponsor, IRB, or regulatory agency requests withdrawal of the participant
7. Any other reason relating to the participant's safety or integrity of the study data as determined by the Safety Assessment Committee (SAC)

Participants who withdraw or are withdrawn from the study may be replaced. Participants who withdraw or are withdrawn from the study cannot subsequently rejoin the study.

If a participant withdraws or is withdrawn from the study for reasons related to safety, the study Sponsor-Investigator and SAC will be informed immediately.

If the participant withdraws consent for disclosure of further information, the Sponsor-Investigator may retain and continue to use any collected data before such a withdrawal of consent.

Although a participant is not obliged to give a reason for withdrawing from a study, the investigator should make a reasonable effort to ascertain the reason, while fully respecting the participant's rights.

## **6. Study Assessments and Procedures**

All assessments, and their corresponding administration points, are listed in Table 1.

## 6.1 Pre-Screening Procedures

Participants will have the opportunity to learn about the study through digital recruitment efforts. Interested participants will complete a pre-screening survey to determine preliminary eligibility ahead of consent. Eligible participants at this stage will then proceed to review and sign the eICF.

## 6.2 Screening Assessments and Procedures

### 6.2.1 Identity Verification Call

After passing pre-screening criteria and signing the study eICF, participants will be asked to schedule an identity verification video call with a member of the Lindus Health study team. During this call the designated member of the study team will ask the participant to verify their identity (e.g., show a government issued ID) as well as confirm their contact information and DOB.

### 6.2.2 Demographic Questions

In an effort to ensure equitable access and representation as well as assess clinical efficacy in diverse populations, Woebot Health has researched current best practices and language around demographic data collection, and developed a health equity demographic battery. The demographic battery consists of age, biological sex, gender identity, sexual orientation, race, ethnicity, education, marital status, employment status, living situation, able bodiedness, physical health conditions, and health insurance status.

### 6.2.3 Medical History

#### *Prior and Concomitant Medication and Therapy*

Participants will be asked to complete questions evaluating whether they are currently seeing a mental health professional (i.e., therapist, social worker), whether they are currently taking any psychotropic medications, as well as satisfaction with concurrent mental health treatment.

#### *Psychiatric History*

[figure not shown]
Participants will be asked to complete questions about their history of diagnosed mental health disorders including self-report of a lifetime diagnosis of bipolar disorder and/or a psychotic disorder as well as whether they have current suicidal ideations with plan and/or intent or if they have had a suicide attempt in the past 12 months. Participants will also be asked to endorse whether they have experienced any involuntary inpatient psychiatric hospitalizations within the past 30 days.

[figure not shown]
## 6.3 Primary Endpoint

#### *Working Alliance Inventory (WAI-SR)*

The WAI-SR^5 is a measure of therapeutic bond and consists of a composite score and three subscales; Bond, Goal, and Task. Bond measures the strength of the therapeutic relationship between the client and therapist. Goal measures agreement on the goal of the overall therapeutic program between the client and therapist. Task measures agreement between the client and therapist, regarding the specific activities needed for a therapeutic change to occur such as doing an exercise to ameliorate a specific

symptom3. The present study utilized the validated 12-item Short Revised version (WAI-SR) with minor changes to language, replacing “therapist” with the name of the assigned treatment group.

## 7. Study Stopping Rules

Study procedures will be stopped if the Sponsor-Investigator, in discussion with the SAC and/or IRB as applicable, determines that the number and/or severity of AEs justify putting the study on hold.

The study may resume following the safety review, if the Sponsor-Investigator agrees it is safe to proceed.

The Sponsor-Investigator may initiate study closure at any time, provided there is reasonable cause and sufficient notice is given in advance of the intended termination.

### 7.1 Early Study Termination

The study can be terminated by the Sponsor-Investigator at any time. Reasons for early termination include:

- Study recruitment or retention is too low for the study to provide meaningful results
- Unanticipated, significant, or unacceptable safety risk to participants enrolled in the study
- Decision based on recommendations from Sponsor-Investigator and SAC after review of safety and efficacy data
- Discontinuation of study if Sponsor-Investigator, in collaboration with study team members and SAC, determine from planned analyses that the app is not efficacious or if there are safety concerns.

In making the decision to terminate, the Sponsor-Investigator and SAC will always consider the participants' welfare and safety. Should early termination be necessary, participants must be contacted as soon as possible to conduct EOS assessments, if willing, and treated as a prematurely withdrawn participant. Additional procedures may be provided to ensure that adequate consideration is given to the protection of the participant's interests. The Sponsor-Investigator will be responsible for informing IRB of the early termination of the trial.

## 8. Data and Safety Monitoring

### 8.1 Risk and Benefit Assessment

#### 8.1.1 Risks to Participants

Given that the research aims to enroll participants into a low-risk intervention, we do not anticipate that participation in the study will be associated with elevated risk. [REDACTED]

[REDACTED] The overall evaluation of risk is that it is low.

#### 8.1.2 Procedures for minimizing risk

##### *Misunderstanding the Capabilities of the Application*

DISC-MA is not intended to be a crisis service, however there is the potential that participants may misunderstand the limitations of the app. To mitigate this risk, the study will provide clear information on the capabilities of the app, intended use, and limitations of the app at consent, treatment assignment, and key points throughout. Resources are also accessible within the app as well and will be sent to the participant in the event that they are requested.

##### *Data Breach*

All study data are gathered on either a HIPAA-compliant web platform that resides behind Woebot Health security firewalls or via HIPAA-compliant online platforms, thus actual risk from data breach for study data is low. Research material obtained from human subjects will include self-report questionnaires and conversations and engagement data within the mobile app. All data obtained via Woebot will be encrypted and stored on Amazon Web Services (AWS) and/or Google Cloud Platform; Woebot Health data gathering and storage procedures are compliant with both HIPAA and the European Union's General Data Protection Regulation. Only members of the research team will have access to identifiable study data. De-identified data will be accessible to the product development team (designers, user researchers, and product managers) as well as the research team.

##### *Potential Upset due to Study Procedures*

Foreseeable risks to participants include the possibility that some assessment questions and/or treatment procedures may be upsetting to participants. Experience with similar populations has indicated that the risk of emotional upset during the assessments is low and if it occurred, the upset would likely be temporary and not be serious in nature. Such risks will be minimized by the thoughtful selection of questionnaires. Participants will also be informed that they may withdraw from the study at any time and if requested, appropriate resources will be provided.

There is also a potential risk for upset upon discontinued access to the study intervention at end of treatment/study (Week 4). Participants are informed during the consent process and are reminded at onboarding of how long they will have access to the intervention for. Return to care and other resources are provided upon removing access to DISC-MA.

Participants can refuse and withdraw from participation at any time. If they withdraw consent from the study, they will no longer have access to the study treatment.

### **8.1.3 Benefits**

When evaluating the risks and benefits of the proposed study, it is believed that risks are relatively minimal when compared to the potential [REDACTED] benefits that subjects are likely to receive. The benefits of engaging with DISC-MA include potentially improving mood (anxiety, stress, and/or depression), acquiring practical psychotherapeutic skills (from cognitive behavioral therapy, dialectical behavior therapy, and mindfulness), and receiving psychoeducation about mental health.

Participants who improve mood may derive additional benefits should said mood improvements be associated with other psychological improvements such as interpersonal or occupational functioning. Study of the effectiveness of this intervention will also benefit society more generally by providing data on the utility of Woebot.

## **8.2 Adverse Events**

### **8.2.1 Definitions**

Adverse Event (AE): An AE is any unanticipated medical occurrence in a clinical study participant using an investigational product or from study procedures that does not necessarily have a causal relationship with this product. An AE can therefore be any unfavorable and unintended sign (including an abnormal laboratory finding), symptom, or disease temporally associated with the use of an investigational product, whether or not related to the investigational product.

Serious Adverse Event (SAE): An SAE is any AE that meets any of the following criteria:

- Results in *death*
- Is *life-threatening*
- Requires inpatient *hospitalization* or prolongation of existing hospitalization
- Results in persistent or significant *disability/incapacity*
- Is a *congenital anomaly/birth defect*
- Is an *important medical event* that may not result in death, be life-threatening, or require hospitalization may be considered a serious adverse event when, based upon appropriate medical judgment, they may jeopardize the patient or subject and may require medical or surgical intervention to prevent one of the outcomes listed above.

Unanticipated Problem (UAP): A UAP is an incident, experience, or outcome that meets all of the following criteria:

- Unexpected in nature, severity, or frequency (i.e., not described in study-related documents such as the IRB- or IEC-approved protocol or consent form)
- Related or possibly related to participation in the research (i.e., possibly related means there is a reasonable possibility that the incident experience or outcome may have been caused by the procedures involved in the research)
- Suggests that the research places subjects or others at greater risk of harm (including physical, psychological, economic, or social harm)

An individual AE observed during the conduct of a study may be considered an unanticipated study problem involving risk to human subjects, and reported to the IRB, only if it is unexpected, serious, and would have implications for the conduct of the study (e.g., requiring a significant and, usually, safety-related change in the protocol such as revising the inclusion/exclusion criteria or including a new monitoring requirement or informed consent). Investigators should report possible UAP to the Sponsor and the Sponsor will make a determination for the UAP in the context of the study and any change to the study.

**Adverse Device Effect (ADE):** Any adverse event related to the use of an investigational medical device. This includes any adverse event resulting from insufficiencies or inadequacies in the instructions for use, the deployment, the implantation, the installation, the operation, or any malfunction of the investigational medical device. This also includes any event that is a result of a use error or intentional misuse.

**Unanticipated Adverse Device Effect (UADE):** Any serious adverse effect on the health or safety, or any life-threatening problem or death caused by or associated with a device which was not previously identified in nature, severity or degree of incidence in the protocol, Instructions for Use, Summary of Previous Studies Document, or other sources of information for the investigational product. Additionally, a UADE is any other unanticipated serious problem associated with the investigational device that relates to the rights, safety, or welfare of subjects.

UADEs will include events meeting either A or B as stated below:

*A. Events meeting ALL of the following criteria:*

- Not included in the list of Anticipated Events (refer to protocol section 8.2.2)
- Related (possibly, probably, or definitely) to the investigational device per the site principal investigator
- Serious (meets any of the SAE criteria)

*B. Any other unanticipated serious problem associated with the investigational device that relates to the rights, safety, or welfare of participants.*

**Device Deficiencies:** Inadequacy of a medical device related to its identity, quality, durability, reliability, safety or performance, such as malfunction, misuse or use error and inadequate labeling. The reporting of a Device Deficiency is a Product Complaint.

**Product Complaints:** Any written, electronic, or oral communication that alleges deficiencies related to the identity, quality, durability, reliability, safety, effectiveness, or performance of a device after it is released for distribution.

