### 8.2.2 Previously Noted Adverse Device Effects

Any ADE that is not identified in nature, severity, or is not listed below is considered unanticipated:

- Temporary upset may occur as a result of discontinued access to DISC-MA at the end of the study.
- Given that the study involves use of a smartphone application, there is the small possibility of unintended application outages.

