## 10.3 Safety Endpoints

### 10.3.1 Aims and Endpoints

The safety profile of DISC-MA will be investigated as an exploratory aim and measured through:

- Frequency of AE/SAE/UADEs
  - Spontaneous participant report of safety events that are determined to be an AE/SAE/UADE
  - Direct participant self-report of safety events at the Week 2 and Week 4 survey that are determined to be an AE/SAE/UADE
  - Transcript reviews that detect safety events and are determined to be an AE/SAE/UADE

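### The AE definition in 8.2.1 requires an event to be unanticipated, which contradicts the rest of 8.2.1 and 8.2.2 and could leave foreseeable non-serious harms uncounted

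*Combined protocol and SAP*

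**What the plan says.** Section 8.2.1 opens the AE definition with "An AE is any unanticipated medical occurrence in a clinical study participant using an investigational product". The sentence also takes in occurrences arising from study procedures and requires no causal link. The next sentence is wider: "An AE can therefore be any unfavorable and unintended sign (including an abnormal laboratory finding), symptom, or disease temporally associated with the use".

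Two further definitions in 8.2.1 are built on the AE:

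- SAE: "An SAE is any AE that meets any of the following criteria".
- ADE: "Any adverse event related to the use of an investigational medical device".

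Expectedness then appears again in three places:

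- The UAP paragraph of 8.2.1 lets an individual AE qualify as an unanticipated problem only where it is unexpected and serious and has implications for study conduct.
- UADE criterion A in 8.2.1 requires, among other things, that the event is absent from the anticipated list in 8.2.2.
- Section 8.2.2 states: "Any ADE that is not identified in nature, severity, or is not listed below is considered unanticipated". It lists two items: "Temporary upset may occur as a result of discontinued access to DISC-MA at the end of the study", and for the app itself, "there is the small possibility of unintended application outages".

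Section 8.1.2 separately describes upset from assessment questions or treatment procedures as a foreseeable risk.

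Under 8.3, an event goes on the eCRF if it meets the criteria for an AE, SAE, UAP, UADE or Device Deficiency. The safety endpoint in 10.3.1 is "Frequency of AE/SAE/UADEs", and 10.3.2 reports it as n(%).

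**The concern.** The AE is the counting unit of the safety endpoint. If being unanticipated is part of what makes an event an AE, a harm the sponsor foresaw is not an AE, and so is neither an SAE nor an ADE. Section 8.2.2 would then describe an empty set, since an anticipated ADE could not exist.

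The practical risk is inconsistent classification. One assessor applying the first sentence and another applying the second could code the same event differently, and the AE numerator would depend on who coded it. The harms most exposed are the mild, foreseeable ones, which the protocol itself names as the main risks of taking part. Section 5.3 item 4 and the hold provision in Section 7 also use SAE or AE status, so they rest on a term with two meanings.

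**Working it through.** There is no figure to reproduce: the plan gives no AE rate, no numeric safety threshold and no power calculation. The check is one of set membership.

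**Step 1: the nesting.** By 8.2.1, every SAE is an AE and every ADE is an AE. Any condition on AEs therefore passes to both.

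**Step 2: two readings.**

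- *Narrow* (first sentence taken literally): an anticipated event is not an AE, SAE or ADE.
- *Broad* (second sentence, supported by the UAP paragraph, UADE criterion A and 8.2.2): expectedness plays no part in AE status. It matters only in deciding whether an event is a UAP or UADE.

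Under the narrow reading the expectedness tests for UAPs and UADEs are largely redundant. Under the broad reading they do real work.

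**Step 3: apply both readings to events the documents name.**

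1. *Upset from assessment questions.* It is foreseeable by 8.1.2 and not listed in 8.2.2. The 8.2.2 default, under which unlisted effects are unanticipated, covers device effects only, and a questionnaire is a study procedure. Narrow: not an AE. Nor does another recorded category catch it. It is described in the protocol, so it is not an unexpected problem in nature. It is neither serious nor device-related, so it is not a UADE, and it is not a Device Deficiency. Broad: recorded and counted. This is the cleanest example.
2. *Upset from treatment procedures.* Section 8.1.2 calls it foreseeable, yet as an unlisted device effect it would be deemed unanticipated by 8.2.2. On the narrow reading the two sections give different answers.
3. *Upset on losing access.* It is listed in 8.2.2. Narrow: not an AE. ADE is neither a recorded category in 8.3 nor a counted one in 10.3.1, so nothing replaces the lost entry. Broad: recorded and counted. One limit applies to both readings. AE collection ends at Week 4 (8.3.1), the visit at which Table 1 ends access, so upset arising afterwards is missed either way.
4. *Application outage.* In itself this is not a medical occurrence. It fits Device Deficiency (reliability, malfunction), which 8.3 records whether or not it was expected. Nothing is lost.
5. *A device effect unlisted in 8.2.2, or differing in nature or severity.* It is deemed unanticipated, so the narrow reading does not exclude it.

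**Step 4: effect on the endpoint.** Suppose n counts participants, and let d be the participants whose only AEs are anticipated ones. The narrow reading reports n, the broad reading n + d. Section 10.3.2 names no denominator. If the target of 200 is assumed, each such participant shifts the percentage by 1/200 = 0.5 percentage points. The documents give no basis for a value of d.

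**The case against.** The strongest reply is that the text as a whole points to the broad reading. The second sentence has no expectedness test, the UAP paragraph presupposes that some AEs are expected, and 8.2.2 calls its listed items adverse device effects. Detection is not filtered either: the survey in 8.5.3 asks about changes in mental or physical health generally, and 8.4 sends every potential safety event to the investigator within one business day. A Safety Management Plan that is not public may settle the coding, and part of the risk text in 8.1.1 is redacted.

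Much of this stands. It shows that under-counting is possible rather than certain, and that detection of events does not depend on the disputed word. It does not remove the contradiction. The second sentence is written as a consequence of the first, so it does not clearly override it, and recording and counting depend on classification rather than detection.

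A reader might infer three stronger conclusions, none of which the documents support:

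- *That serious events common in this population, such as admission for worsening depression or anxiety, would escape the SAE count.* No visible text lists a serious event as anticipated. Neither 8.2.2 item is described as serious, and 8.1.2 expects assessment upset to be temporary and not serious.
- *That the hold and discontinuation provisions would fail to operate.* The Section 7 hold is a judgement with no threshold. Section 5.3 (the investigator's duty regarding well-being, and items 3 and 7) and Section 7.1 contain safety grounds that do not depend on AE status.
- *That the definitions fix the count at an extreme: none for loss-of-access upset, or an ADE entry for every user after an outage.* The first treats the narrow reading as settled. The second fails because ADEs are not a recorded or counted category and an outage is already a Device Deficiency.

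**Conclusion.** The concern holds as an internal contradiction in the safety definitions. The word *unanticipated* in the first sentence of the AE definition conflicts with the second sentence, the UAP paragraph, UADE criterion A and the 8.2.2 list. If it is followed literally, foreseeable non-serious harms would be neither recorded nor counted as AEs.

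The documented effect falls on AE counts rather than SAE counts, and its size cannot be derived. The conclusion assumes that at least some assessors apply the first sentence as written and that the Safety Management Plan does not already correct it. Safety is an exploratory aim here, so the trial's main purpose is not threatened. The correction is still worth making, because the unit being counted should have one meaning.

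**What to change.** 1. In 8.2.1, replace the phrase *unanticipated medical occurrence* with *unfavorable medical occurrence, whether or not anticipated*.
2. State that expectedness is assessed only when deciding whether an event is a UAP or a UADE.
3. State that events listed in 8.2.2 are recorded and counted as AEs when they meet the AE definition.
4. Read Section 5.3 item 4 and Section 7 with the corrected definition, so that AE and SAE mean the same thing throughout. No change to those rules is proposed here.

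The 8.2.2 list can stay as it is. UADE criterion A refers to it, so removing the outage item would change the UADE test. Tabulating anticipated and unanticipated AEs separately is a reporting preference and not needed for this correction.

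The cost is one phrase, a clarifying sentence or two, the amendment step required by Section 14, and a check that the Safety Management Plan uses the same wording. No new data collection is needed. The downside is that reported AE counts may be somewhat higher. The change will not recover upset that arises after AE collection closes at Week 4.
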